Once informed consent is obtained, study participants will be randomized into two different groups: low dose spinal bupivacaine with EVE (BE), and standard-dose spinal bupivacaine (B). Spinal anesthesia will be administered via CSE in routine fashion by a qualified anesthesia provider that is independent of this study. The primary outcome will be total PACU time defined as the time from admission to PACU until the time patient meets PACU discharge criteria (Modified Bromage scale of < 2, blood pressure and heart rate within 20% of baseline, return of baseline oxygenation status as measured by pulse oximetry, alert with baseline mentation, pain well controlled) (Modified Bromage scale: 0-ability to maintain leg lift for prolonged period; 1- ability to lift legs briefly; 2- ability to bend knees; 3- ability to wiggle toes; 4- no movement of lower extremities). Secondary outcomes will be: (1) time until sensory level of T10 achieved, (2) degree of peak motor block after spinal placement (3) time until return of motor function (Modified Bromage score < 2), (4) duration of the block (defined as time from placement until PACU discharge criteria met), (5) quality of the block (as determined by any pain reported during surgery and/or the need to supplement through the epidural) and (6) patient satisfaction (based off of a 0-10 scale). A total of 40 patients will be recruited for the study.

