#### **11.0 STATISTICAL CONSIDERATIONS**

**Demographic Variables:** Age, weight, height, past medical history, procedure type.

**Control Variables:** Group B (10 mg of preservative-free isobaric bupivacaine and 12.5 mcg of fentanyl) vs Group BE (5 mg of preservative-free isobaric bupivacaine and 12.5 mcg of fentanyl with 10 ml of sterile saline through epidural)

**Study Variables:** The primary endpoint is the time until PACU discharge requirements are met. The secondary endpoints are time elapsed to achieve T10 sensory level, degree of peak motor blockade, time elapsed until motor block regresses to modified Bromage score < 2, duration of the spinal block, and patient satisfaction score.

**General Data Analysis:** All demographic and clinical variables with continuous measures will be expressed as means and standard deviations; categorical factors will be expressed as proportions. For non-normal data, the medians and interquartile ranges will be displayed. The distribution of the continuous factors will be examined using the Kolmogorov-Smirnov test. For data that are normally distributed, One-way analysis of variance (ANOVA) will be used to compare the two types of anesthesia. For data that are not normally distributed, the Kruskal-Wallis test will be used for comparisons. Chi-square and Fisher's exact tests will be used to analyze categorical data. For all comparisons, a p-value less than 0.05 will be considered statistically significant.

**Primary Outcome Analysis.** The primary endpoint for this study is the length of time until PACU discharge requirements are met. One-way ANOVA (or the Kruskal-Wallis test, as appropriate) will be used to assess whether PACU length of stay is significantly associated with type of spinal anesthesia. Linear regression will also be used to evaluate the relationship between method of spinal anesthesia and PACU length of stay, while controlling for relevant clinical and demographic variables.

**Secondary Outcome Analysis:** One-way ANOVA will also be used to compare groups on time to achieve T10 sensory level, degree of peak motor blockade, time elapsed until motor block regresses, and patient satisfaction.

**Additional Data Analysis:** N/A

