**Statistical Power and Sample Size Estimates:** Approximately 40 subjects (20 per group) are expected to be enrolled in this study. Assuming a standard deviation of 20 minutes for PACU length of stay, a study with this sample size will have approximately 80.7% power to detect a 20 minute difference and approximately 98.9% power to detect a 30 minute difference in PACU length of stay between Group B and Group BE.

**Study Population Availability:** Approximately 3-5 of these procedures are performed per week, which equals about 200 cases per year. About 80% of these cases will be done under spinal anesthesia for a total of 160 per year. Assuming a 50% enrollment rate, it should take 7 to 8 months to complete enrollment.

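### The stated power of 80.7% and 98.9% is that of 17 patients per group, not of the planned 20 per group

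*Combined protocol and SAP*

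**What the plan says.** The sample-size paragraph of Section 11.0 (Statistical Power and Sample Size Estimates) begins: "Approximately 40 subjects (20 per group) are expected to be enrolled in this study". It continues "Assuming a standard deviation of 20 minutes for PACU length of stay" and concludes that "this sample size will have approximately 80.7% power to detect a 20 minute difference and approximately 98.9% power" to detect a 30-minute difference. The summary in Section 1.0 gives the same total: "A total of 40 patients will be recruited for the study".

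The test and significance level are stated earlier in Section 11.0. For the primary outcome, "One-way ANOVA (or the Kruskal-Wallis test, as appropriate) will be used to assess whether PACU length of stay is significantly associated" with the type of spinal anesthesia. The threshold is general: "For all comparisons, a p-value less than 0.05 will be considered statistically significant". Sidedness is not stated.

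The documents give no dropout rate, evaluable number, replacement rule, rank-test efficiency factor or power formula. The 50% rate in the paragraph on population availability concerns how many eligible patients will enrol, not how many will be lost afterwards.

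**The concern.** The power figures are attached to a study of 40 patients in two groups of 20, but that study does not have that power under the assumptions printed beside it. This paragraph is the plan's only justification of its size.

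Two readings are open, and they tolerate different losses:

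- **40 is the number analysed.** Power is then understated, and several patients could be lost before power for 20 minutes fell to the printed figure.
- **40 is the number enrolled and 34 the number analysed.** The printed power then already uses up a 15% loss allowance that the plan never mentions. Any further loss soon takes power below 80%.

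The rest of the plan does not help to choose. Section 8.0 says only that the statistician assesses the data once enough participants have been recruited.

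**Working it through.** **Inputs**

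- Group size: 20 and 20 (Section 11.0; total of 40 also in Section 1.0).
- Standard deviation: 20 minutes (Section 11.0).
- Differences: 20 and 30 minutes (Section 11.0), so the standardised differences are d = 20/20 = 1.0 and d = 30/20 = 1.5.
- Alpha: 0.05 (Section 11.0). Two-sided is assumed, because the F-test of a two-group one-way ANOVA is the two-sided t-test.

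**Formula**

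For n per group, the degrees of freedom are 2n − 2 and the noncentrality is δ = d × √(n/2). Power is the probability that a noncentral t with that δ falls outside ± the 97.5% point of the central t.

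**The stated design, n = 20**

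- Degrees of freedom 38, critical value 2.024.
- 20 minutes: δ = 1.0 × √10 = 3.162; power 86.90%.
- 30 minutes: δ = 1.5 × √10 = 4.743; power 99.61%.

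The plan's figures are not reproduced. The gaps are 86.9 − 80.7 = 6.2 points and 99.6 − 98.9 = 0.7 points.

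**Which group size gives the printed pair?**

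| n per group | Power, 20 min | Power, 30 min |
|---|---|---|
| 16 | 78.1% | 98.4% |
| **17** | **80.70%** | **98.87%** |
| 18 | 83.0% | 99.2% |
| 19 | 85.1% | 99.4% |
| 20 | 86.9% | 99.6% |

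At n = 17 (degrees of freedom 32, critical value 2.037, δ = 2.915 and 4.373), both figures match the printed decimals. A loss of 15% from 40 leaves 40 × 0.85 = 34, which is 17 per group.

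**Other routes to the printed pair**

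| Variant | 20 min | 30 min | Comment |
|---|---|---|---|
| One-sided t-test, n = 20 | 92.8% | 99.9% | further away |
| Normal approximation, n = 20 | 88.5% | 99.7% | further away |
| Normal approximation, n = 16 | 80.7% | 98.9% | matches, but not at 20 per group |
| Rank test, usual efficiency under normality (3/π ≈ 0.955), n = 20 | 85.3% | 99.5% | no match |
| Rank test simulated on normal data, n = 20 (20,000 runs) | about 85% | 99.3% | no match |
| Rank test, worst-case efficiency 0.864 (20 × 0.864 = 17.28) | 81.4% | 99.0% | close; not stated in the plan |
| Alpha lowered to about 0.028, n = 20 | 80.7% | 99.2% | second figure fails; contradicts 0.05 |
| Split of 12 and 28 | 80.6% | 98.9% | close; contradicts 20 per group |
| SD of about 21.8, n = 20 | 80.7% | 98.9% | contradicts SD of 20 |

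Every route that reaches or comes close to both figures needs an input that the plan omits or contradicts.

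With 20 per group and an SD of 20 minutes, the difference detectable with 80% power is 18.2 minutes.

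**The case against.** The strongest reply concerns the rank test. The plan allows Kruskal-Wallis in place of ANOVA and does not say which test the power refers to. If the worst-case rank-test efficiency of 0.864 was applied to 20 per group, the effective size is 17.28. Rounded down to 17 whole patients, that gives exactly the printed pair. On this reading the figures do belong to 20 enrolled per group, the fault is an unstated adjustment rather than bad arithmetic, and a 15% loss allowance is only one guess at the cause. Replacing the figures with 86.9% and 99.6% would then discard a deliberately cautious number.

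The reply also notes that the error is on the safe side, that the 30-minute figure is nearly right, and that the text says approximately throughout.

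Part of this stands. The cause cannot be settled from the documents, and the 15% loss is an inference from 34/40. The direction is conservative, and no analysis or patient number changes.

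It does not rescue the paragraph. The rank-test reading needs a worst-case factor that the plan never mentions, plus rounding down; unrounded it gives 81.4% and 99.0%. With the usual efficiency for normal data, the rank test at 20 per group has about 85% power. So neither planned test yields the printed pair from the stated inputs. A figure printed to one decimal place and 6.2 points off is not covered by approximately.

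**Conclusion.** The concern holds. Under the plan's own inputs, 20 per group has 86.9% power for a 20-minute difference and 99.6% for 30 minutes. The printed 80.7% and 98.9% are the power of 17 per group by the planned ANOVA. Either the power or the sample-size basis is therefore wrong as written.

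This rests on a two-sided test, equal groups, normal data with a common SD of 20 minutes, and no unstated adjustment. The 20-minute figure carries the finding; the 30-minute discrepancy alone would be negligible.

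The consequence is limited. If all 40 are analysed, the trial has more power than claimed. What must be corrected is that the only stated power does not belong to the stated size, so the losses the design can absorb cannot be read from the plan.

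**What to change.** Rewrite the power sentence in Section 11.0 so that each figure is tied to the number analysed. Suggested wording:

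> With 20 analysed patients per group, a standard deviation of 20 minutes and a two-sided alpha of 0.05, the two-group ANOVA has 86.9% power for a 20-minute difference and 99.6% for a 30-minute difference. With 17 evaluable patients per group (a 15% loss from 40 enrolled), power is 80.7% and 98.9%.

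If 17 evaluable per group was the intended basis, say so and state the loss allowance. If a rank-test adjustment was intended instead, name the test and the efficiency factor, and give the figures that follow from them. The test, alpha and sidedness should be stated in every case.

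The cost is one sentence. Enrolment, the planned analysis and the timeline do not change.

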## 12.0 PATIENT SAFETY AND DATA SECURITY MONITORING

**Assessment of Level of Risk:**

Low

**Oversight of this investigation will be provided by:**

Oversight of this investigation will be provided by the Principal Investigator as well as the UAB department of Human Subjects Research Committee.

**The mechanisms for HIPAA compliance [including a detailed electronic personal health information (PHI) data path]:**

Data will be collected on the IRB-approved data sheet. These forms will be stored in a locked cabinet in the PI's locked office. Data from the forms will be transferred to our HIPPA-compliant, password-protected database.

## 13.0 REPORTING ADVERSE EVENTS

Adverse events will be reported to the IRB.

## APPENDIX A (Starting as a new page) (For Internal Departmental Use Only)

## STUDY BUDGET AND FUNDING SOURCES

Study Title:

